15.2.2 TEAEs and Serious AEs by severity

Population: SAF and PP

Stratification: Table: Add the strata as needed in case subjects with dose modification exceeding 20% based on enrolled population as per section 7.3:

- a. Subjects on 1.5 mg only by Primary SOC and PT in decreasing order and Severity
- b. Subjects on 0.75 mg only by Primary SOC and PT in decreasing order and Severity
- c. Subjects with any dose modification* by Primary SOC and PT in decreasing order and Severity

* Subjects who have received at least one dose of 1.5 mg and at least one dose of 0.75 mg

Statistics: Treatment emergent AEs and Serious adverse events (SAEs) by severity will be summarized as (n=number of subjects, m=number of events and %=percentage of subjects) for table.

16. Safety laboratory tests

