9.4.2. Primary Endpoints Analysis

AEs (deaths, SAEs, TEAEs, and hypoglycemia, including severe hypoglycemia)

Frequency and percentage of AE occurrence (including deaths, SAEs, TEAEs, hypoglycemia, including severe hypoglycemia and GI disorders) will be presented for the study duration using safety population.

The proportion of patients with AEs and SAEs occurring within the duration of the study (24 weeks) after being administered dulaglutide 1.5 or 0.75 mg will be presented.

The proportion of patients with AEs, TEAEs, and SAEs occurring within the duration of the study (24 weeks) after being administered dulaglutide 1.5 or 0.75 mg and 95% CIs will be estimated based on normal approximation.

The incidence of AE (death, SAE, and TEAE) will be summarized. The rate per year will be assessed using a negative binomial model with the log of the study treatment exposure time as an offset variable.

The incidence of hypoglycemic AEs will be summarized. The number of hypoglycemic events per subject over the study period will be analyzed as continuous variables and will be summarized (mean, median, SD, SE, minimum, and maximum).

The rate per year of hypoglycemic events, that is, the number of hypoglycemic events per patient-year (365.25 days) will be assessed using a negative binomial model, with baseline HbA1c and baseline insulin usage as covariates and the log of the study treatment exposure time as an offset variable.

The incidence of AEs will be calculated based on the number of new AEs out of the total eligible population using the following formula:

$$\text{Number of new AEs post intervention/Total eligible population *100.}$$

Exposure-adjusted AE incidence will be presented by the severity and preferred term for the primary analysis.

It is defined as

Number of patients with new or worsened AEs during treatment period

Patient-year exposure/365.25

Patient-year exposure is counted in days up to the AE (or end of time at risk for subjects without AE).

Incidence of gastrointestinal AEs

The incidence of GI AEs per week will be plotted over time from baseline up to 24 weeks. The proportion of subjects with at least 1 GI AE will be plotted from baseline up to Week 24. A plot of prevalence by severity (mild, moderate, or severe) for nausea, vomiting, and diarrhea over the 24-week period will be provided for the rate of GI AEs.

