Assessment of Intensity

The investigator will assess the intensity of each AE and SAE reported during the study and assign it to 1 of the following categories:

- Mild: A type of AE that is usually transient and may require only minimal treatment or therapeutic intervention. The event does not generally interfere with usual activities of daily living.
- Moderate: A type of AE that is usually alleviated with additional specific therapeutic intervention. The event interferes with usual activities of daily living, causing discomfort but poses no significant or permanent risk of harm to the research participant.
- Severe: A type of AE that interrupts usual activities of daily living, significantly affects clinical status, or may require intensive therapeutic intervention. An AE that is assessed as severe should not be confused with an SAE. Severe is a category utilized for rating the intensity of an event, and both AEs and SAEs can be assessed as severe.

An event is defined as "serious" when it meets at least 1 of the predefined outcomes as described in the definition of an SAE, NOT when it is rated as severe.

Assessment of Causality

- The investigator is obligated to assess the relationship between study intervention and each occurrence of each AE/SAE. The investigator will use clinical judgment to determine the relationship.
- A “reasonable possibility” of a relationship conveys that there are facts, evidence, and/or arguments to suggest a causal relationship, rather than a relationship cannot be ruled out.
- Alternative causes, such as underlying disease(s), concomitant therapy, and other risk factors, as well as the temporal relationship of the event to study intervention administration, will be considered and investigated.
- The investigator will also consult the IB for dulaglutide and Product Information for insulin glargine and insulin lispro in their assessment.
- For each AE/SAE, the investigator **must** document in the medical notes that they have reviewed the AE/SAE and have provided an assessment of causality.
- There may be situations in which an SAE has occurred, and the investigator has minimal information to include in the initial report to Sponsor or designee. However, it is very important that the investigator always assesses the causality for every event before the initial transmission of the SAE data to the Sponsor or designee.

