14.2 Analysis

Population: SAF and PP

Stratification: Table: Add the strata as needed in case subjects with dose modification exceeding 20% based on enrolled population as per section 7.3:

a. Subjects on 1.5 mg only by ATC and PT

b. Subjects on 0.75 mg only by ATC and PT

c. Subjects with any dose modification* by ATC and PT

* Subjects who have received at least one dose of 1.5 mg and at least one dose of 0.75 mg

Listing: By subject

Statistics: Prior and concomitant medication will be summarized separately as (frequency, percentages) for table and listing will be presented.

15. Adverse events**15.1 Variables and derivations**

Adverse Events (AEs) will be coded using MedDRA central coding dictionary, Version (refer to DMP for dictionary version).

For the definition of Adverse events (AE) and Serious adverse event (SAE) refer to the protocol section 10.3.

TEAEs are defined as events that are newly reported after the first study drug treatment or are reported to have worsened in severity after the first study drug treatment.

In section 24 Appendix 2 the algorithm is given for calculation of partial date imputation for adverse events (AEs), and it will be used for partially missing adverse event start and end date imputation.

The following parameters will be summarised for the overview of participants' adverse events:

- Any AEs
- Any TEAEs
- Related TEAEs
- Severity of TEAEs (Mild, Moderate, Severe, Life threatening and Death)
- Outcome of AEs (Recovered or resolved, Recovering, or resolving, Not recovered or not resolved, Recovered, or resolved with sequelae, Fatal and Unknown)
- Serious AEs
- AEs leading to Discontinuation from the study
- AEs leading to Death
- Related AEs leading to Death

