17.2 Analysis

Population: SAF and PP

Stratification: Table: Add the strata as needed in case subjects with dose modification exceeding 20% based on enrolled population as per section 7.3:

- a. Subjects on 1.5 mg only
- b. Subjects on 0.75 mg only
- c. Subjects with any dose modification*

* Subjects who have received at least one dose of 1.5 mg and at least one dose of 0.75 mg

Listing: by subject, visit and each vital sign parameter

Statistics: The vital signs except temperature will be summarised as actual and change from baseline (number of patients, mean, SD, median, minimum, maximum, and interquartile ranges) for table. The listing will be presented for all vital sign parameters. Mean \pm SD plot will be provided for Vital sign parameters.

18. Primary endpoint**18.1 Incidence of AEs (deaths, SAEs, TEAEs, and hypoglycemia, including severe hypoglycemia)****18.1.1 Variables and derivations**

Variables:

- All AEs will be captured in the “Adverse Events” eCRF form.
- Hypoglycemia events will be captured in the “Hypoglycemic events” eCRF form.

Derivations:

- To identify incidence of deaths the eCRF question “the severity of the adverse event” = “Death” will be used from AE form.
- If the question “the adverse event serious” is indicated as “Yes” then corresponding events will be considered as SAEs.
- If the AE started on or after the first treatment administration date will be considered as TEAEs.
- Hypoglycemia events will be captured and identified using the “Hypoglycemic events” eCRF form.
- If the question “Did subject have any Hypoglycemic events” is “Yes” on “Hypoglycemic events” eCRF form and the question “the adverse event serious” is indicated as “Yes” on the AE eCRF form, then corresponding events will be considered as severe hypoglycemia events.
- The incidence of AEs= Number of new AEs post intervention/Total eligible population *100.
- The incidence of hypoglycemic AEs= (Number of new hypoglycemic AEs post intervention/Total eligible population)*100.
- Number of hypoglycemic events per patient-year (365.25 days)= Number of patients with hypoglycemic events /365.25
- Exposure Adjusted AE Incidence= Number of patients with new or worsened AEs during treatment period / (Patient-year exposure/365.25)
- Patient-year exposure is counted in days up to the AE (or end of time at risk for subjects without AE).

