Exposure-adjusted AE incidence will be presented by the severity and preferred term for the primary analysis.

Additionally, all the analysis will be repeated for the below mentioned subgroups:

- age (<65 year and \geq 65 year)
- HbA1c (<8.5 and \geq 8.5)
- Sex (Female and male)
- BMI category (<27 kg/m²) and \geq 27 kg/m²)

18.2 Proportion of patients reporting AEs and SAEs between baseline and Week 24

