18.3.2 Analyses

Population: FAS and PP

Stratification: Table: Add the strata as needed in case subjects with dose modification exceeding 20% based on enrolled population as per section 7.3:

- a. Subjects on 1.5 mg only
- b. Subjects on 0.75 mg only
- c. Subjects with any dose modification*

* Subjects who have received at least one dose of 1.5 mg and at least one dose of 0.75 mg

Statistics: The incidence of GI AEs will be summarised and a plot of prevalence by severity (mild, moderate, or severe) for nausea, vomiting, and diarrhoea over the 24-week period will be provided for the rate of GI AEs. Plot of severity with reference to time will be provided by subjects.

Three Cox proportional hazard models, each with covariates for baseline HbA1c and baseline insulin use, will be used to model the time to the first onset of nausea, vomiting, or diarrhoea TEAE,

respectively. Hazard ratio and 95% confidence interval and p-value will be presented for the covariates for the overall data. If additional analysis based of dose stratification is done, the Hazard ratio and 95% confidence interval and p-value will also be presented for dose with 1.5 mg as the reference group.

Subjects who do not experience any GI AEs during 24 weeks and discontinued before 24 weeks of period will be considered as censored.

The Kaplan Meier plot (unadjusted) will be presented for median time to first onset of nausea, vomiting, or diarrhoea TEAE, respectively along with corresponding 95% confidence interval. Y axis will represent the survival probability of the GI AEs and X axis will represent the duration in days of GI event occurred from first dose administration. Number of subjects at risk will be presented in the plot.

Additionally, all the analysis will be repeated for the below mentioned subgroups:

- age (<65 year and \geq 65 year)
- HbA1c (<8.5 and \geq 8.5)
- Sex (Female and male)
- BMI category (<27 kg/m²) and \geq 27 kg/m²)

19. Secondary endpoint**19.1 Mean change in HbA1c from baseline to Week 24****19.1.1 Variables and derivations**

Variables:

- HbA1c results

Derivations:

- HbA1c results between visit baseline visit 2 (week 0) and visit 8 (week 24) will be used.

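### The SAP's AE severity item adds 'Life threatening' and 'Death' to the protocol's three intensity levels with no mapping rule, which affects the 'Severe' rows, the GI plot and the death count

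*SAP*

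**What the plan says.** - **Protocol 10.3.4, Assessment of Intensity.** The instruction to sites reads: "The investigator will assess the intensity of each AE and SAE reported during the study and assign it to 1 of the following categories". The categories are mild, moderate and severe. The section adds that "An AE that is assessed as severe should not be confused with an SAE", and that both AEs and SAEs can be rated severe. Death and life-threatening events are seriousness criteria in protocol 10.3.2, not grades of intensity.
- **SAP 15.1.** The AE overview uses five levels: "Severity of TEAEs (Mild, Moderate, Severe, Life threatening and Death".
- **SAP 18.1.1.** The list in 15.1 is not a slip, because the primary endpoint relies on the extra level: "To identify incidence of deaths the eCRF question “the severity of the adverse event” = “Death” will be used from AE form".
- **SAP 15.2.2 and 18.1.2.** The by-severity tables ("Treatment emergent AEs and Serious adverse events (SAEs) by severity will be summarized") name no levels. A primary-endpoint output is also split this way: "Exposure-adjusted AE incidence will be presented by the severity and preferred term for the primary analysis".
- **SAP 18.3.2 and protocol 9.4.2.** The GI display has three levels in both documents. The SAP has "a plot of prevalence by severity (mild, moderate, or severe) for nausea, vomiting, and diarrhoea over the 24-week period", and the protocol has "A plot of prevalence by severity (mild, moderate, or severe) for nausea, vomiting, and diarrhea over the 24-week period will be provided".
- **SAP section 5.** It states that the protocol's methods were adopted without change. Neither document says how five levels become three.

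**The concern.** A severity item has exclusive levels. An event recorded as 'Life threatening' or 'Death' is therefore not recorded as 'Severe', although severe is the highest level the protocol offers. A 'Severe' row built on five levels then describes a narrower class of event than the protocol's definition. The three-level GI plot has no level in which to show an event from either added category.

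The mismatch also works the other way. An investigator who follows the protocol text may grade a fatal event 'Severe'. The SAP 18.1.1 rule looks only for severity equal to 'Death' and would not count it. Deaths are a named component of the first primary endpoint, and the SAP also plans a yearly rate for them, so this is the more direct consequence.

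**Working it through.** **1. Planning figures.** Protocol 9.6 gives 250 screened, 20% screen failure and 20% dropout. 250 × (1 − 0.20) = 200 treated, and 200 × (1 − 0.20) = 160 at the end. Both stated figures reproduce. Neither document gives an expected rate for severe, life-threatening or fatal AEs.

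**2. Where an event goes under each grading.**

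| Event and grade recorded | 'Severe' row (15.2.2, 18.1.2) | Three-level GI plot, if nausea, vomiting or diarrhoea | Death count under 18.1.1 |
|---|---|---|---|
| Life-threatening, graded 'Severe' | in | shown | not applicable |
| Life-threatening, graded 'Life threatening' | out; own row | no level for it | not applicable |
| Fatal, graded 'Severe' | in | shown | missed |
| Fatal, graded 'Death' | out; own row | no level for it | counted |

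For a fatal event, neither grading puts it in all three places. Graded 'Severe', it leaves the death count; graded 'Death', it leaves the 'Severe' row.

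**3. Size in the 'Severe' row.** Let S be the patients who would be severe on the protocol's scale and k those of them recorded in an added level. With 200 treated, the row shows (S − k)/200 instead of S/200, a relative difference of k/S. S and k are assumptions.

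| S (three-level row) | k = 0 | k = 1 | k = 2 | k = 4 |
|---|---|---|---|---|
| 6 (3.0%) | 3.0% (0%) | 2.5% (17%) | 2.0% (33%) | 1.0% (67%) |
| 10 (5.0%) | 5.0% (0%) | 4.5% (10%) | 4.0% (20%) | 3.0% (40%) |
| 20 (10.0%) | 10.0% (0%) | 9.5% (5%) | 9.0% (10%) | 8.0% (20%) |

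The relative difference is in parentheses.

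**4. Chance that the issue arises.** For an assumed true risk p of a life-threatening or fatal event per patient, the chance of at least one such patient among 200 is 1 − (1 − p)^200:

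| p | Chance of at least one |
|---|---|
| 0.1% | 18% |
| 0.5% | 63% |
| 1% | 87% |
| 2% | 98% |

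**5. Size in the death count.** If D patients die and d of them have the fatal event graded 'Severe', the 18.1.1 rule finds D − d. With D = 1 and d = 1 it finds none. With D = 0 or d = 0 nothing is lost. The documents give no value for D or d.

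**The case against.** A reader might infer that severe AEs are under-counted and the primary safety results biased low. The documents do not support that. In a five-level table, life-threatening and fatal events have their own rows beside 'Severe' and can be added back. They stay in the TEAE totals. SAP 15.1 and 15.2.1 also report SAEs and AEs leading to death, and 15.1 reports outcome, including 'Fatal'. The listings in 15.2 show severity and outcome event by event. The exposure-adjusted incidence is split more finely, not distorted, and protocol 9.1 sets no hypothesis. For the tables this objection stands: the problem is labelling and comparability with the protocol.

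A reader might also infer that the worst GI events will vanish from view. Only the prevalence plot could lose one, and only if nausea, vomiting or diarrhoea were graded life threatening or fatal. Protocol 4.2 describes these events as mostly mild to moderate and self-limiting, so the case is remote. Such an event would still enter the GI incidence summary and, as a first onset, the Cox and Kaplan-Meier analyses. It could also appear in the by-subject severity plot, which is not limited to three levels.

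That sites would grade the same event differently cannot be shown either, because the eCRF and its completion guidance are not among the documents. Nor does protocol 10.3.4 say that life-threatening or fatal events map to 'Severe'. That is a convention, which follows from severe being the top of its scale.

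None of this answers the missing mapping rule or the death derivation. SAP 15.1 does not say which field identifies AEs leading to death. If it is the outcome field, that table and the 18.1 death count could disagree.

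**Conclusion.** The conflict is real, undeclared and cheap to remove. It rests on two readings: that the eCRF severity item has the two added levels, as SAP 15.1 and 18.1.1 indicate, and that its levels are exclusive.

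The effect is zero if no event is life-threatening or fatal. Otherwise its size depends on how many such events there are and how they are graded. The percentages in the working only illustrate this and are not estimates. For the by-severity tables and rates, the result is a 'Severe' row that is not comparable with the protocol's definition, with no event lost from the report. For the GI plot, loss of an event is possible but unlikely. For deaths, the 18.1.1 rule can miss one that was graded as the protocol instructs, and in a study of about 200 patients a single missed death would matter to a primary safety component.

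**What to change.** 1. In SAP 15.1, 15.2.2, 18.1.2 and 18.3.2, state that for by-severity tables, rates and the GI plot the levels 'Life threatening' and 'Death' are mapped to 'Severe', the protocol's highest level. Describe this as an SAP convention. Do it in a derived variable, so that the grade as collected is not overwritten and still appears in listings.
2. In SAP 18.1.1, identify deaths from AE outcome 'Fatal', together with the death record among the End of Study reasons listed in SAP 10.1, instead of from the severity item. This must accompany step 1, because an overwritten severity item would leave the present rule with no deaths to find.
3. Show life-threatening events on a separate line, taken from the grade as collected. The SAP describes only a yes/no seriousness item, so an itemised seriousness criterion cannot be assumed.
4. Record the difference between the two scales in SAP section 5.

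The cost is a few sentences of SAP text and a little extra programming. No new data need be collected.

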16.1 Variables and derivations

All laboratory parameters mentioned in protocol section 10.5 will be summarized.

Quantitative laboratory measurements reported as “< X”, i.e., below limit of quantitation, or “> X”, i.e., above the upper limit of quantification, will be converted to X for quantitative summaries, but will be presented as recorded, i.e., as “< X” or “> X” in the data listings.

